3.7.2. Multiple Comparison / Multiplicity

Not applicable.

3.7.3. Subgroup Analysis

Subgroup analyses of efficacy endpoints will be performed for each of the following categories:

- Bipolar disorder
 - Change from baseline in IWQOL-Lite score by visit
 - Weight, metabolic responses, waist circumference, safety AEs and shift in CGI score in 2 points or 5 compared to those hospitalized due to AEs will be presented by visit.
- Sex (male, female)
- Age (<18 years, ≥ 18 years)
- Age (<30 years, ≥ 30 years)
- Race (Black or African American, Non-Black or Non-African American)

- Baseline BMI (<25 kg/m², ≥25 kg/m²)
- Region (US, Non-US)
- Among those who completed study at 24 months, 36 months, and 48 months, change in weight, waist circumference and metabolic responses will be summarized.
- For those who switched from ALKS3831-A307 to ALKS3831-A308 change from baseline in CGI, weight, waist circumference and lipid levels by visit will be summarized.

Descriptive statistics will be provided for the subgroups listed above.

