13.3. Definition of Serious Adverse Event

An SAE is any AE, occurring at any dose and regardless of causality, that:

• Results in death

- Is life-threatening. The subject is at immediate risk of death from the reaction as it occurs. This does not include reaction that, had it occurred in a more severe form, might have caused death
- Requires inpatient hospitalization or prolongation of existing hospitalization
- Results in persistent or significant disability/incapacity (eg, a substantial disruption of a person's ability to conduct normal life functions)
- Is a congenital anomaly/birth defect

Important medical events that may not result in death, be immediately life threatening, or require hospitalization may be considered to be SAEs when, based upon appropriate medical judgment, they may jeopardize the patient or subject and may require intervention to prevent one of the other outcomes listed above. Admission to an inpatient unit or hospital for a nonmedical or nonbehavioral reason (ie, social stay admission) during the study in the absence of untoward medical occurrence will not be considered an SAE, but will be reported as an AE.

Hospitalization due to worsening of behavioral health related issues should be reported as an SAE.

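### SAP 3.7.3 sets bipolar subjects beside a group picked for AE hospitalization; read as a group comparison, its overall AE/SAE and CGI contrasts cannot be interpreted

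*SAP*

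**What the plan says.** SAP 3.7.3 names bipolar disorder as a subgroup category. Sex, age, race, BMI and region are listed with their levels; bipolar disorder is not. It has two sub-items.

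- The first, "Change from baseline in IWQOL-Lite score by visit", names no comparator.
- The second is a single sentence: "Weight, metabolic responses, waist circumference, safety AEs and shift in CGI score in 2 points or 5", continuing "compared to those hospitalized due to AEs will be presented by visit".

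The section closes with "Descriptive statistics will be provided for the subgroups listed above". No bipolar versus non-bipolar contrast is written anywhere in the SAP. SAP 3.7.4 asks for metabolic changes by subgroup without naming levels.

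Protocol 13.3 lists among the SAE criteria an AE that "Requires inpatient hospitalization or prolongation of existing hospitalization", and adds: "Hospitalization due to worsening of behavioral health related issues should be reported as an SAE". It makes an exception for social-stay admissions, which are recorded as AEs but not as SAEs. SAP 3.8.1 counts an event as treatment-emergent from first dose to 7 days after last dose.

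**The concern.** A comparator should be defined by something known at baseline. This one is defined by an event after baseline, and that event is itself an AE and, with the stated exceptions, an SAE. If AEs are compared with such a group, its overall incidence is set by the way it was picked. If CGI shifts are compared with it, some of its members are there because their psychiatric condition worsened, which is what the CGI-S rates. Bipolar subjects would then tend to look safer and more stable than the reference column, whatever the drug does.

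Bipolar I disorder is named in the primary objective, and the study has no control arm. A reader looking for evidence in that diagnosis would therefore turn to descriptive displays such as this one. It is the only explicit comparison that the SAP writes for bipolar subjects.

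**Working it through.** **No figure to reproduce.** The documents give no rate, effect size or error rate for this analysis. The check is a logical one, followed by an illustration.

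**1. What is fixed.** Let H be the group hospitalized due to an AE.

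- P(any AE | H) = 1, because membership requires an AE.
- P(SAE | H) = 1 under Protocol 13.3, except for social-stay admissions if the derivation counts them as AE hospitalizations.
- If only TEAEs are counted, an event starting more than 7 days after last dose falls outside both statements.
- These are cumulative incidences. The incidence in any one visit interval is not fixed.

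If p is the any-AE rate in bipolar subjects, the difference is p - 1, which cannot exceed zero.

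**2. Illustration with no true bipolar effect.** N = 500 is the approximate planned size. All other inputs are assumptions: 20% bipolar; any-AE rate 40%, 60% or 80%; AE hospitalization 2%, 5% or 10%; one preferred term at 5% and a weight change with SD 7, both independent of hospitalization. Each of the nine settings was simulated 1,000 times.

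| Assumed any-AE rate | p - 1 | Simulated mean difference | Run closest to zero |
|---|---|---|---|
| 40% | -60 points | -60 points | -43 points |
| 60% | -40 points | -40 points | -21 points |
| 80% | -20 points | -20 points | -6 points |

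The hospitalized group stood at 100% in every run. The rate of SAEs by hospitalization in bipolar subjects was 2% to 10%, against 100%.

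**3. What is not fixed.** In the same runs, the preferred-term and weight differences averaged about zero.

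| Assumed hospitalization rate | Hospitalized, N × rate | Of whom bipolar, × 20% | SD of preferred-term difference | SD of weight difference |
|---|---|---|---|---|
| 2% | 10 | 2 | 7.5 to 8.0 points | 2.3 to 2.5 |
| 5% | 25 | 5 | 4.8 to 4.9 points | 1.5 to 1.6 |
| 10% | 50 | 10 | 3.5 to 3.6 points | 1.1 to 1.2 |

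The zero averages follow from the assumed independence. They show that these results are not determined by the definition of H. They do not show that the results would be unbiased.

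**4. CGI.** Suppose a share s of H was admitted for psychiatric worsening, and those subjects score d points worse on the CGI-S than they otherwise would. The comparator mean is then worse by s × d with no bipolar effect at all. The documents give neither s nor d, so the direction can be stated but not the size.

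**5. The CGI criterion.** SAP 3.7.1, Tables 1 and 2, defines shifts as moves between three categories (scores of 3 or less, 4, and 5 or more), reported at 1, 3, 6 and 12 months. The sentence in 3.7.3 refers to 2 points or 5, by visit. That could mean a 2-point change, a score of 5, or either. It matches neither table.

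**The case against.** The strongest reply is that the sentence is badly written rather than a design choice. The comparison may attach only to the nearest item, the CGI shift, in which case no AE contrast is ordered. It may also mean setting CGI worsening beside hospitalization in the same subjects, which is sensible and close to the fix below. Mock shells are kept in a separate document and may settle the intent. The output is descriptive, no decision rests on it, and the bipolar subjects' own by-visit results would be shown either way.

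Most of this stands. Under the CGI-only reading the AE argument falls away, although the comparator is still partly selected for worsening. The same-subjects reading is reasonable, but the sentence does not say it.

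A reader might infer more than the documents support:

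- **That the whole AE result is predetermined.** Only the comparator's overall incidence and the sign of the difference are. SAP 3.8.1 reports AEs mainly by system organ class, preferred term, severity and relationship, and those profiles are not fixed.
- **That weight, waist and metabolic results are fixed too.** Nothing in the definition of the group does that.
- **That hospitalized bipolar subjects sit in both groups, or that a subject admitted late fills the hospitalized column from the first visit.** Table 10 puts Month 30 at Visit 31, so 29 scheduled post-baseline visits (Visits 2 to 30) precede it for monthly measures. But the SAP does not say whether membership is fixed or time-varying, or whether the groups overlap.
- **That the bipolar part of the primary objective rests on this table.** The SAP does not say so.

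**Conclusion.** Wrong as written, minor severity. Under either group-comparison reading, the text orders a contrast with a group selected on a post-baseline AE outcome; it does not merely leave out a detail.

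- If AEs are compared, the overall any-AE and SAE contrast says nothing about bipolar subjects, subject to the social-stay and TEAE-window exceptions.
- If the CGI shift is compared, the contrast leans towards making bipolar subjects look stable, by an amount that the documents do not allow one to estimate.

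The 20 to 60 point gaps are illustrations under assumed AE rates, not predictions. No error rate or primary conclusion is affected.

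**What to change.** In SAP 3.7.3:

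1. Delete the comparison with hospitalized subjects.
2. Report the number and percentage of bipolar subjects in the Safety Population who were hospitalized due to an AE. State whether social-stay admissions, and events more than 7 days after last dose, count.
3. Within bipolar subjects, cross-tabulate that outcome against a defined CGI-S worsening criterion. It should replace the 2-points-or-5 wording and state the change or score required and the visits over which it is judged.
4. Present weight, waist, metabolic and AE results for bipolar subjects by visit, without a hospitalized reference column.
5. If a between-group display is wanted, name a comparator defined at baseline, such as non-bipolar subjects, and list the outcomes it covers. Protocol 5.1 describes ALK3831-A307 as the antecedent study that takes in bipolar I disorder, so the display should also state which antecedent studies supply the comparator.

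The cost is a change of SAP wording and one replaced table shell. No new data are needed. What is lost is a side-by-side column whose overall AE/SAE and CGI entries could not be interpreted.

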3.7.4. Other Endpoints

Other endpoints include:

- Absolute change from baseline in fasting lipids (triglycerides, LDL, HDL, total cholesterol, fasting glucose, hemoglobin A1c (HbA1c), insulin) by subgroups
- Absolute change from baseline in fasting lipids (triglycerides, LDL, HDL, total cholesterol, fasting glucose, hemoglobin A1c (HbA1c), insulin) by antecedent study at End of the treatment
- Absolute change from baseline in BMI by visit
- BMI shift:
 - Proportion of subjects shifting from BMI <25 kg/m² at baseline to BMI ≥25 kg/m² by visit
 - Proportion of subjects shifting from BMI <30 kg/m² at baseline to BMI ≥30 by visit

3.8. Safety Analysis

All safety endpoints will be summarized for the Safety Population.

3.8.1. Adverse Events

Incidence of treatment-emergent AEs (TEAEs) will be analyzed as a safety endpoint. Adverse events will be coded by System Organ Class and Preferred Term using the Medical Dictionary for Regulatory Activities (MedDRA[®]) Version 21.0 or higher. The verbatim term will be included in the AE listings.

An AE (coded by preferred term) will be considered a TEAE if the event is newly occurring or worsening on or after the date of first dose of study drug and within 7 days after the last dose of study drug in this study.

An overview table, including number of subjects with TEAEs, AEs leading to treatment discontinuation, study drug related TEAEs, and SAEs will be provided.

The number and percentage of subjects reporting TEAEs during the treatment period will be presented for the following categories:

- System organ class and preferred term
- Preferred term, and including the following subset:
 - TEAEs experienced by $\geq 2\%$ of subjects
- System organ class, preferred term, and severity
- System organ class, preferred term for severe TEAEs
- System organ class, preferred term, and relationship
- System organ class, preferred term for study drug related TEAEs

If the same preferred term occurred more than once for the same subject, the subject will be counted only once for that preferred term using the most severe and most related occurrence for the summarization by severity and by relationship to the study drug.

In addition, the number and percentage of subjects reporting AEs during the safety follow-up period will be tabulated by the system organ class and preferred term.

Subgroup analysis by age (<40 years vs ≥ 40 years), sex (Female vs Male) and race (Black or African American, White, and Other) will be performed for TEAEs during the treatment period by preferred term.

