^aVisits will occur monthly throughout the 48-month Treatment period. Subjects will start the study on the equivalent olanzapine dose to what they maintained at the end of the antecedent study. The dose may be adjusted to either 5/10, 10/10, 15/10, or 20/10mg throughout the study period based on investigator discretion, and such dose adjustments will require subjects to visit the study site.

Number of Subjects Planned: Approximately 500 subjects

Main Criteria for Inclusion: Subjects will have completed the treatment period in one of the following antecedent studies within 7 days: ALK3831-A304, ALK3831-A306, or ALK3831-A307. Subjects will have potential to benefit from ALKS 3831 in the opinion of the investigator, and agree to use an acceptable method of contraception during the study and until 30 days after any study drug administration, unless surgically sterile or post-menopausal.

Main Criteria for Exclusion: Subjects may be excluded based on positive tests for drugs of abuse at study entry, any finding that would compromise the subject's safety or their ability to fulfill the study requirements, pregnancy or breastfeeding, or employment by (or relationship to an employee of) the study sponsor, clinical research organization, or study site.

Investigational Product, Dosage, Duration, and Mode of Administration: ALKS 3831 refers to the fixed dose combination of olanzapine and samidorphan. ALKS 3831 will be supplied as a coated bilayer tablet containing 5, 10, 15, or 20 mg olanzapine and 10 mg samidorphan. The tablet will be taken by mouth once daily, preferably at bedtime, for at least 24 but not more than 48 months. The study is planned to be open until approximately the 4th quarter 2022 or until regulatory action. Therefore, depending on when a subject is enrolled, the duration of participation in this study will vary.

Reference Therapy, Dosage, Duration, and Mode of Administration: None

Duration of Study: The total study duration will be up to 49 months, including a treatment period of 24 to 48 months and a 4-week safety Follow-up period.

Criteria for Evaluation:

Safety and Tolerability: The following parameters will be collected to measure safety and tolerability throughout the study:

- AEs (including clinically significant abnormal ECG findings)
- Vital signs (oral temperature, respiratory rate, blood pressure, and heart rate)
- Weight and waist circumference
- Clinical laboratory parameters (biochemistry, hematology, and urinalysis)

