8. STUDY DESIGN

8.1. Overall Study Design and Plan

This is a multicenter, open-label study to evaluate the long term safety, tolerability, and durability of treatment effect of ALKS 3831 in subjects with schizophrenia, schizophreniform disorder, or bipolar I disorder. Subjects that have completed the antecedent studies (ALK3831-A304, ALK3831-A306, or ALK3831-A307) within the past 7 days will be eligible to enroll in this study.

[figure not shown]
Subjects enrolled in the study will be started on the same olanzapine dose that they had maintained at the end of the antecedent study. Available doses of ALKS 3831 will be 5/10, 10/10, 15/10, and 20/10 mg. Subjects may be titrated to a different dose after the start of the study at the Investigator's discretion. Dosing will be flexible throughout the study; however, frequent adjustments are discouraged. Dose adjustments will only be performed on-site at the study center. Subjects requiring dose adjustments between scheduled visits will need to arrange an unscheduled visit.

Safety assessments will include AE monitoring, clinical laboratory testing, vital signs, body weight, ECGs, and the Columbia-Suicide Severity Rating Scale (C-SSRS). Psychiatric symptoms will be evaluated using the CGI-S scale. Additional assessments will include Impact of Weight on Quality of Life-Lite Questionnaire (IWQOL-Lite).

The duration of the treatment period will vary by subject, between 24 and 48 months, or until regulatory action; duration will vary by subject. The study completion is targeted for the 4th quarter of 2022. After the last subject is enrolled, the end date of the study will be set to occur 24 months later (approximately the 4th quarter of 2022), and subjects will be informed of the target completion date. The total study duration will be up to 49 months including a treatment period of 24 to 48 months and a 4-week safety Follow-up period and return to their normal standard of care once their participation has ended. A schematic of the study design is provided in Figure 1.

The end of trial is defined as the date of the last subject's last visit.

Figure 1: Study Design Schematic

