3.8.1.1. Deaths, Serious and Other Significant AEs

The number and percentage of subjects who have serious adverse events (SAE) and AEs leading to discontinuation from the treatment will be summarized by system organ class and preferred term. And the number and percentage of subjects reporting SAEs will be summarized by system organ class, preferred term, and relationship to study drug.

By-subject listings will be provided for SAEs, AEs leading to treatment discontinuation and AEs leading to death.

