Visit 29	Month 28	Day 785	[771, 798]
Visit 30	Month 29	Day 813	[799, 826]
Visit 31	Month 30	Day 841	[827, 854]
Visit 32	Month 31	Day 869	[855, 882]
Visit 33	Month 32	Day 897	[883, 910]
Visit 34	Month 33	Day 925	[911, 938]
Visit 35	Month 34	Day 953	[939, 966]
Visit 36	Month 35	Day 981	[967, 994]
Visit 37	Month 36	Day 1009	[995, 1022]
Visit 38	Month 37	Day 1037	[1023, 1050]
Visit 39	Month 38	Day 1065	[1051, 1078]
Visit 40	Month 39	Day 1093	[1079, 1106]
Visit 41	Month 40	Day 1121	[1107, 1134]
Visit 42	Month 41	Day 1149	[1135, 1162]
Visit 43	Month 42	Day 1177	[1163, 1190]
Visit 44	Month 43	Day 1205	[1191, 1218]
Visit 45	Month 44	Day 1233	[1219, 1246]
Visit 46	Month 45	Day 1261	[1247, 1274]
Visit 47	Month 46	Day 1289	[1275, 1302]
Visit 48	Month 47	Day 1317	[1303, 1330]

Analysis Visit to be Mapped to	Target Study Month	Target Visit Date	Visit Window
Visit 49	Month 48	Day 1345	[1331, 1351]

Visit Day is calculated as visit date – date of the first dose of study drug + 1. 1 month=28 days

Table 11: Visit Window Definition for Vital Signs, Lab and IWQOL-Lite Data

Analysis Visit to be Mapped to	Target Study Month	Target Visit Day	Visit Window
Visit 4	Month 3	Day 85	[2, 126]
Visit 7	Month 6	Day 169	[127, 210]
Visit 10	Month 9	Day 253	[211, 294]
Visit 13	Month 12	Day 337	[295, 378]
Visit 16	Month 15	Day 421	[379, 462]
Visit 19	Month 18	Day 505	[463, 546]
Visit 22	Month 21	Day 589	[547,630]
Visit 25	Month 24	Day 673	[631,714]
Visit 28	Month 27	Day 757	[715,798]
Visit 31	Month 30	Day 841	[799, 882]
Visit 34	Month 33	Day 925	[883,966]
Visit 37	Month 36	Day 1009	[967,1050]
Visit 40	Month 39	Day 1093	[1051,1134]
Visit 43	Month 42	Day 1177	[1135,1218]
Visit 46	Month 45	Day 1261	[1219,1302]
Visit 49	Month 48	Day 1345	[1303,1351]

Visit Day is calculated as visit date – date of the first dose of study drug + 1. 1 month=28 days

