APPENDIX 6. COVID-19 ANALYSIS

Pandemic has resulted in certain disruptions in the study conduct since early 2020, including site closure, delayed study drug supply, subjects discontinuation and missing assessments. These impacts were limited in scope upon review of the protocol deviations, and also confounded by the initiation of new regions. Sites in Ukraine and Russia were first initiated in March 2020 and July 2020. Therefore, only descriptive statistics will be provided to explore the potential impact of the pandemic on the primary and secondary objectives of the study. The following subgroup analysis (before vs during pandemic) will be conducted:

- Disposition
- Demographics and Baseline Characteristics
- Protocol Deviation
- Primary Efficacy Endpoint
- Key Secondary Endpoints
- TEAE
- SAE

Subjects enrolled before 01 Mar 2020 will be grouped as before pandemic, and subjects enrolled after this date will be grouped as during pandemic. While the pandemic has started in various regions a few weeks apart, a single cutoff date will be applied.

Signature Page for CLIN_ALK3831-A308-sap

Approved	Name: PPD Capacity: Other Date: 04-Dec-2023 19:59:22 GMT+0000
Approved	Name: PPD Capacity: Clinical Date: 04-Dec-2023 23:33:04 GMT+0000
Approved	Name: PPD Capacity: Clinical Date: 07-Dec-2023 12:34:29 GMT+0000
Approved	Name: PPD Capacity: Other Date: 07-Dec-2023 13:00:52 GMT+0000

Alkermes® Confidential Information

Document REG-026019

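### TEAEs and SAEs are planned as crude percentages without person-time although follow-up varies by design, which biases the before/during-pandemic contrast

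*SAP*

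**What the plan says.** The Protocol's safety endpoint list (Section 13.1) begins with AE incidence. SAP Section 3.8.1 turns this into counts and percentages of subjects: "The number and percentage of subjects reporting TEAEs during the treatment period will be presented for the following categories". An event counts as treatment-emergent from first dose until "within 7 days after the last dose of study drug in this study", so each subject's window is as long as that subject's own exposure. Section 3.8.1.1 uses the same measure: "The number and percentage of subjects who have serious adverse events (SAE) and AEs leading to discontinuation from the treatment will be summarized". Section 3.8.1.2 asks for the incidence of AESIs by preferred term and names no denominator. Neither document plans person-years, a rate, a cumulative incidence or a fixed time window for TEAEs.

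Follow-up is unequal by design. Protocol Section 8.1 states "The duration of the treatment period will vary by subject, between 24 and 48 months, or until regulatory action" and "After the last subject is enrolled, the end date of the study will be set to occur 24 months later", and the Synopsis adds that "depending on when a subject is enrolled, the duration of participation in this study will vary". Subjects who withdraw are not replaced (Protocol Section 7.4) and remain in the Safety Population.

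SAP Appendix 6 plans a before/during-pandemic comparison that includes TEAEs and SAEs: "Subjects enrolled before 01 Mar 2020 will be grouped as before pandemic, and subjects enrolled after this date will be grouped as during pandemic". Its list of analyses contains no exposure summary for the two groups.

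Two provisions bear on the point. SAP Section 3.6.2 summarises exposure overall and by demographic subgroups that include age, sex and race. SAP Section 3.7.1 applies Kaplan-Meier to discontinuation due to AE.

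**The concern.** A crude percentage divides subjects with an event by all subjects, whatever their time at risk. When time at risk ranges from a few weeks (early dropout) to 48 months, the result mixes many durations and estimates the incidence at none of them. For a study whose purpose is long-term safety, that weakens the reading of a named safety endpoint.

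A contrast between groups is worse off when follow-up differs between them, because the group observed longer shows the higher percentage even if the underlying risk is the same. In Appendix 6 this is built in. With a common study end and a 48-month cap, no subject enrolled before the cutoff has a shorter maximum follow-up than a subject enrolled after it. A reader could take a higher TEAE or SAE percentage in the before group as a difference in safety, or in reporting, between the two periods. Appendix 6 would not supply the exposure figures needed to judge that.

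**Working it through.** The plan gives no event rate, dropout rate or power figure, so there is none to reproduce. The schedule arithmetic does reproduce. With "1 month=28 days" (SAP Section 6.1), Month 24 is 24 × 28 + 1 = Day 673 and Month 48 is 48 × 28 + 1 = Day 1345, as in SAP Tables 10 and 11.

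**Inputs from the documents**
- 24 study months = 672 days = 1.84 years; 48 study months = 1344 days = 3.68 years.
- Cutoff 01 Mar 2020; study end about the fourth quarter of 2022, set 24 months after the last enrolment.

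**Assumptions**
- Study end in December 2022, so the earliest subjects in the during group have 34 calendar months (34/12 = 2.83 years).
- Maximum follow-up in the during group spread evenly from 1.84 to 2.83 years.
- Maximum follow-up in the before group either 3.68 years for everyone (case A) or spread evenly from 2.83 to 3.68 years (case B).
- The same constant event hazard λ in both groups, 0.05 or 0.10 per year.
- Dropout hazard d of 0, 0.20 or 0.40 per year. At 0.40, 1 − exp(−0.40 × 1.84) = 52% have left by 24 study months.
- The 7-day tail after the last dose is ignored.

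**Formula.** For a maximum follow-up T, the expected crude proportion is

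P(T) = λ/(λ + d) × [1 − exp(−(λ + d)T)],

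averaged over T where follow-up is spread.

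**Worked example (λ = 0.05, d = 0)**
- Before, case A: 1 − exp(−0.05 × 3.68) = 16.8%.
- During: 1 − [exp(−0.05 × 1.84) − exp(−0.05 × 2.83)] / [0.05 × (2.83 − 1.84)] = 11.0%.
- Ratio: 1.53, with no difference in risk.

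**All combinations, before vs during (ratio)**

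| λ per 100 PY | d per 100 PY | Case A | Case B |
|---|---|---|---|
| 5 | 0 | 16.8% vs 11.0% (1.53) | 15.0% vs 11.0% (1.36) |
| 5 | 20 | 12.0% vs 8.8% (1.36) | 11.1% vs 8.8% (1.26) |
| 5 | 40 | 9.0% vs 7.2% (1.25) | 8.5% vs 7.2% (1.19) |
| 10 | 0 | 30.8% vs 20.8% (1.48) | 27.8% vs 20.8% (1.33) |
| 10 | 20 | 22.3% vs 16.7% (1.33) | 20.8% vs 16.7% (1.24) |
| 10 | 40 | 16.8% vs 13.7% (1.23) | 16.0% vs 13.7% (1.17) |

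The ratios run from 1.17 to 1.53, or about 1.2 to 1.5.

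**Overall table.** The display cut of 2% of subjects in SAP Section 3.8.1 shows the same dependence on time. Without dropout it corresponds to −ln(0.98)/1.84 = 1.10 per 100 person-years over 24 study months, but −ln(0.98)/3.68 = 0.55 over 48.

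**With person-time.** Under a constant hazard, expected first events equal λ × expected person-time at risk, whatever T and d are. The rate is then λ in both groups and the expected rate ratio is 1.00.

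**The case against.** The strongest reply is that nothing inferential depends on these percentages. The study is open-label and single-arm, and SAP Section 3.7.2 treats multiplicity as not applicable. Appendix 6 confines itself to descriptive exploration and acknowledges confounding by newly opened regions, which a rate would not remove. Protocol Section 14.6 itself specifies numbers and percentages, so the SAP follows its protocol. The mock tables sit in a separate document that was not available. All of this stands. It makes the point one of interpretation rather than error control, but it does not make unequal follow-up harmless in a table whose purpose is to compare two groups.

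Stronger readings are tempting but not supported:
- A reader might set exactly 24 against exactly 48 months and infer a distortion of 1.83 (16.8% vs 30.8% at 10 per 100 person-years without dropout). No SAP subgroup is defined that way, and the enrolment-date split gives the smaller range above.
- A reader might infer that the age, sex and race contrasts are distorted too. That requires exposure to differ between those groups, which the documents do not show. The exposure tables of SAP Section 3.6.2 would reveal such a difference, though they would not adjust for it.
- A reader might infer that comparison with the antecedent studies is spoiled. SAP Sections 3.8.1 to 3.8.1.2 plan no such TEAE comparison.
- A reader might infer that no AE analysis respects follow-up. Discontinuation due to AE already has a Kaplan-Meier analysis.

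**Conclusion.** The point holds, chiefly for Appendix 6. As written, the before/during contrast of TEAEs and SAEs compares groups with unequal maximum follow-up and supplies no exposure figures for them. With identical true risk the before group's percentage would be about 1.2 to 1.5 times the during group's. That size rests on event rates of 5 to 10 per 100 person-years, constant hazards, dropout of 0 to 40 per 100 person-years equal in both groups, a December 2022 end, and evenly spread follow-up where stated. None of the rates comes from the documents. The distortion is smaller for early-onset or very common events and under heavier dropout. A later study end with the 48-month cap unchanged would also narrow the gap.

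For the overall TEAE, SAE and AESI tables there is no between-group bias, but the percentage has no stated duration attached. The age, sex and race tables are affected only conditionally. No test or error rate is involved, so this is a recommended improvement in reporting and does not invalidate the plan.

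**What to change.** Keep the crude percentages. In SAP Sections 3.8.1, 3.8.1.1 and 3.8.1.2 and in Appendix 6, add the number of subjects with a first event per 100 person-years at risk. Time at risk runs from first dose to the first event or, if there is none, to last dose + 7 days. Report this for TEAEs, SAEs and AESIs overall, for the Appendix 6 split, and in the age, sex and race tables. State that the before/during-pandemic comparison rests on these rates, add an exposure summary for the two groups, and record the addition in SAP Section 5.

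The dates needed (first dose, last dose, AE onset) are already required by SAP Sections 3.6.2 and 3.8.1, so no new data are collected. The costs are:
- Person-time to first event must be derived separately for each preferred term, which is more programming than a single extra column.
- The rate assumes a roughly constant hazard. For early-onset events it should be read beside the crude percentage, or beside cumulative incidence at fixed times such as 6, 12 and 24 months.
- The region confounding that Appendix 6 acknowledges remains and should be stated with the results.
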